## LIST OF ABBREVIATIONS

ACCORD	Academic and Clinical Central Office for Research & Development - Joint office for The University of Edinburgh and Lothian Health Board
CI	Chief Investigator
CRF	Case Report Form
GCP	Good Clinical Practice
ICH	International Conference on Harmonisation
F-GP1	Fluoride-18 labelled glycoprotein-1
PI	Principal Investigator
QA	Quality Assurance
REC	Research Ethics Committee
SOP	Standard Operating Procedure
PET	Positron Emission Tomography
CT	Computed Tomography

## **1 INTRODUCTION**

### **1.1 BACKGROUND**

#### **1.1.1 Background of coronary artery disease and acute myocardial infarction**

Coronary artery disease remains the leading cause of death worldwide, with more than 23 million annual deaths estimated to occur by 2030 (1). The introduction of high-sensitivity cardiac troponin measurement has revolutionised the identification and management of patients presenting with acute chest pain and myocardial infarction. However, elevated cardiac troponin concentrations can result from both ischaemic (myocardial infarction) or non-ischaemic (myocardial injury) causes. Moreover, the further subclassification of myocardial infarction relies on the underlying aetiology of infarction which is often not readily apparent and remains a diagnostic challenge.

#### **1.1.2 Universal definition of myocardial infarction**

Acute myocardial infarction is defined as cardiomyocyte injury and necrosis in a clinical setting consistent with acute myocardial ischaemia. The fourth universal definition of myocardial infarction describes five subtypes of acute infarction (2). Type 1 myocardial infarction is characterised by underlying atherosclerotic plaque disruption (rupture, ulceration, fissuring, erosion, or calcific nodules) resulting in intraluminal thrombosis, distal coronary embolisation and intraplaque haemorrhage that ultimately cause myocyte necrosis (3, 4). In contrast, type 2 myocardial infarction is classified as an ischaemic myocardial injury secondary to oxygen supply and demand mismatch, and importantly is not a consequence of atherosclerotic plaque rupture and coronary atherothrombosis. However, some causes of type 2 myocardial infarction do involve intracoronary thrombus including coronary thromboembolism and spontaneous coronary artery dissection. Currently, invasive coronary angiography remains the primary modality to identify patients presenting with plaque related disruption and coronary thrombosis, ultimately providing the distinction between type 1 and type 2 myocardial infarction. However, it is not always definitive (5) and only 10-20% of patients presenting with type 2 myocardial infarction undergo further investigations to identify the presence of underlying coronary artery disease or to exclude coronary atherothrombosis (6). Indeed, we recently demonstrated comprehensive cardiac imaging and coronary angiography that identified two thirds of patients had previously unrecognised underlying coronary artery disease, and this resulted in diagnostic reclassification of many patients (7). These standard techniques were however unable to determine whether this plaque was implicated in the presentation or simply a bystander finding. A non-invasive imaging technique to reliably detect intracoronary thrombus and facilitate this distinction would therefore be of major clinical value.

#### **1.1.3 Imaging intracoronary thrombosis**

At present, invasive coronary angiography is the primary modality used to detect the presence of intracoronary thrombus in patients presenting with acute myocardial infarction, through an abrupt occlusion of the coronary artery or a filling defect in partially occluded vessels. This approach has high specificity but low sensitivity for detection of intracoronary thrombus, necessitating the introduction of adjunctive invasive coronary intravascular imaging including angioscopy, intravascular ultrasound and optical coherence tomography to improve rates of identification of

coronary thrombosis and atherothrombosis (8). Intravascular ultrasound-based studies have indicated an incidence of plaque disruption of 30-40% in patients with myocardial infarction and non-obstructive coronary arteries (9, 10), although this imaging technique cannot differentiate between echo-lucent plaques and acute thrombus (8, 11). Optical coherence tomography has replaced intravascular ultrasound as the gold standard in high-resolution cross-sectional imaging of the arterial intima, providing a more detailed assessment of coronary artery dissection and thrombus formation (12). However, these invasive techniques are not always available, have limitations in respect to assessing smaller or stenosed vessels, and only provide circumstantial evidence of the presence of a thrombus based on the characteristic appearances of the images (13-15). As such, atherothrombotic events may be missed, resulting in misdiagnosis and, importantly, a missed opportunity to establish patients on appropriate treatment and secondary prevention.

#### **1.1.4 Uncertain role of coronary thrombosis in myocardial infarction**

An accurate diagnosis is imperative for establishing subsequent appropriate therapeutic intervention in patients with myocardial infarction. Patients presenting with type 1 myocardial infarction require short-term anticoagulation as well as medium-term dual antiplatelet therapy, in conjunction with other secondary prevention therapies. For most patients with type 2 myocardial infarction, the above strategy would be both ineffective and potentially harmful, such as in patients with bleeding associated anaemia. However, intracoronary thrombus formation underpins certain causes of type 2 myocardial infarction including coronary thromboembolism and spontaneous coronary artery dissection. Accurate identification of intracoronary thrombus is a central tenet in both the diagnosis of type 1 myocardial infarction, and in the differentiation of the various aetiologies underlying type 2 myocardial infarction.

##### **1.1.4.1 Myocardial infarction with non-obstructive coronary arteries**

Co-existing coronary artery disease is common in patients with myocardial infarction and non-obstructive coronary arteries, with plaque disruption being the key trigger of acute myocardial infarction in many cases (3, 4, 9). Myocardial infarction and non-obstructive coronary arteries was first documented over 75 years ago when pathological studies reported evidence of myocardial necrosis in the absence of coronary atherosclerosis (16, 17). Its recognition in clinical practice remains more recent, and it comprises a heterogeneous group of vascular or myocardial disorders, occurring in 5-15% of patients presenting with acute myocardial infarction (18-20). Compared to patients with obstructive coronary artery disease, patients with myocardial infarction and non-obstructive coronary arteries are younger (21, 22), more likely to be female, and have specific genetic and ethnic predispositions (23-25). Interestingly, the prevalence of traditional coronary artery risk factors including dyslipidaemia, hypertension and diabetes mellitus is lower in patients with myocardial infarction and non-obstructive coronary arteries (12, 14-16).

Myocardial infarction and non-obstructive coronary arteries has defined criteria as outlined by the European Society of Cardiology in 2017 (26) and the American Heart Association/American College of Cardiology in 2019 (19). To fulfil the diagnosis, patients must present with (i) acute myocardial infarction as defined by the fourth universal definition of myocardial infarction (2), (ii) non-obstructive coronary arteries on angiography (no coronary artery stenosis  $\geq$  50%), and (iii) no specific alternative diagnosis for the clinical presentation. Only ischaemic causes of acute myocardial infarction are now included in the underlying aetiology of myocardial infarction and

non-obstructive coronary arteries. This includes patients presenting with either type 1 or type 2 myocardial infarction but excludes those with takotsubo cardiomyopathy and myocarditis. Although this has simplified the diagnostic work-up of this patient cohort, there remains a high degree of variability in the way patients with suspected myocardial infarction and non-obstructive coronary arteries are investigated and treated, because it is a diagnosis of exclusion. The identification and management of these patients will depend on local practice and resources, where there may be limited access to more advanced diagnostic testing. This is likely one of the contributory factors underlying a recent analysis demonstrating that patients with myocardial infarction and non-obstructive coronary arteries had a higher one-year adjusted mortality than patients with myocardial infarction and obstructive coronary artery disease (20). As such, there is a clinical need to improve the accuracy in the identification, investigation, and management of this patient population.

#### 1.1.4.2 Coronary thromboembolism

Coronary thromboembolism results in myocardial infarction and non-obstructive coronary arteries if it involves the microcirculation or if the epicardial coronary thrombus is not associated with atherosclerotic coronary artery disease (19). Underlying aetiologies can range from atrial fibrillation, hypercoagulable states, inherited thrombophilia, paradoxical embolism, valvular vegetations, valvular calcifications and cardiac tumours (19, 27). As this subtype of event typically involves smaller calibre coronary vessels, their identification using catheter-based techniques is limited by the inability to access smaller vessels due to the size and physical limitations of the intravascular probes. A more sensitive novel and non-invasive imaging modality that can more accurately assess small calibre coronary vessel thrombosis would be of great clinical value to identify coronary thrombosis events resulting in type 2 myocardial infarction.

#### 1.1.4.3 Spontaneous coronary artery dissection

Spontaneous coronary artery dissection is an uncommon cause of acute myocardial infarction, with a predominance in younger (<50 years) women (28, 29). Myocardial ischaemia is driven by obstruction to coronary blood flow, secondary to separation of medial and adventitial coronary vascular walls, with associated intramural haematoma resulting in protrusion into the coronary arterial lumen. The coronary arteries can appear normal or near normal on coronary angiography, due to gradual tapering of the vessel, and this is commonly a missed diagnosis. Moreover, the prevalence of iatrogenic catheter-induced coronary artery dissection is reported to be increased in patients with spontaneous coronary artery dissection, meaning that many clinicians are reluctant to perform intravascular imaging in patients with this suspected diagnosis (30). Consequently, the true incidence of spontaneous coronary artery dissection is likely to be underestimated (19, 29).

### **1.1.5 Non-invasive imaging of coronary thrombus - Pilot data**

We have recently used positron emission tomography (PET) with computed tomography (CT) coronary angiography to identify intracoronary thrombus using a novel radiotracer, F-GP1. This radiotracer is highly selective and specific for the activated glycoprotein IIb/IIIa receptor on activated platelets (31-33). As part of a previous BHF-funded Clinical Research Training Fellowship ([name]; FS/CRTF/20/24086) and Project Grant (PG/19/40/34422), we have demonstrated that F-GP1 has specificity for the detection of intravascular thrombosis in a range of

cardiovascular conditions (34, 35). We have recently undertaken studies in patients with coronary atherothrombosis in acute type 1 myocardial infarction (35). This was the first demonstration that non-invasive imaging can identify *in vivo* intracoronary thrombus in patients presenting with acute myocardial infarction, and for this work, [name] was awarded the European Society of Cardiology Young Investigator Award in 2021. We have confirmed the high selectivity and specificity of  $^{18}\text{F}$ -GP1 binding to activated platelets within fresh human thrombus and coronary thrombectomy specimens, and importantly we have observed  $^{18}\text{F}$ -GP1 uptake only occurs within the culprit coronary arteries of those with acute myocardial infarction (35). For example, in patients with triple vessel disease, coronary  $^{18}\text{F}$ -GP1 uptake was only seen at the site of the culprit lesion. We have also demonstrated preliminary findings of focal  $^{18}\text{F}$ -GP1 uptake at the site of spontaneous coronary artery dissection, coronary thromboembolism (36) and extra-coronary thrombus including unrecognized left ventricular and atrial thrombus, as well as infarct-related intramyocardial  $^{18}\text{F}$ -GP1 uptake. This changed both the diagnosis (type 1 reclassified as type 2 myocardial infarction) and the treatment (initiation of anticoagulation) of patients presenting with acute myocardial infarction. These data demonstrate the feasibility of identifying patients with intracoronary thrombus and type 1 myocardial infarction, and those with type 2 myocardial infarction caused by spontaneous coronary artery dissection and coronary thromboembolism. Importantly the pattern of  $^{18}\text{F}$ -GP1 distribution differs among these three conditions, allowing their differentiation. This technique holds major promise in aiding the classification of myocardial infarction, especially in patients with myocardial infarction and non-obstructive coronary arteries or where the presence of coronary thrombosis is unclear.

## **1.2 RATIONALE FOR STUDY**

With the evolving complexity in modern diagnostic criteria and treatments, it has become increasingly important to determine the aetiology of acute myocardial infarction and specifically determine the presence of intracoronary thrombosis. This has major implications for treatment decisions and patient outcome. However, there are currently no techniques that can reliably determine the presence of intracoronary thrombus throughout the coronary circulation. Here, we will assess a promising highly sensitive and accurate technique to determine the contribution of coronary thrombosis in patients presenting with uncertain or difficult to diagnose causes of myocardial infarction. This will potentially provide a completely novel approach that could provide major insights into the diagnosis, investigation and treatment of these patients.

## **2 STUDY OBJECTIVES**

### **2.1 OBJECTIVES**

#### **2.1.1 Primary Objective**

The primary objective of this study is to establish the origin, frequency and distribution of activated platelets and thus thrombotic causes of myocardial infarction in patients presenting with myocardial infarction with non-obstructive coronary arteries

#### **2.1.2 Secondary Objectives**

To inform the pathophysiology and understanding of acute myocardial subtypes, by providing additional mechanistic information regarding the presence of intracoronary activated platelets and thrombosis.

## **2.2 ENDPOINTS**

### **2.2.1 Primary Endpoint**

The primary endpoint will be the degree and location of platelet activation as determined by the target to background ratio of F-GP1.

### **2.2.2 Secondary Endpoints**

The secondary endpoints will include measuring the presence of platelet activation in acute myocardial infarction with non-obstructive coronary arteries and identifying the presence and site of platelet activation in thrombosis-related coronary causes of type 2 myocardial infarction.

## **3 STUDY DESIGN**

This will be a prospective observational case-control cohort study

## **4 STUDY POPULATION**

### **4.1 NUMBER OF PARTICIPANTS**

We will recruit two patient populations after invasive coronary angiography has been completed. We have established comparator control populations including 50 patients with stable coronary artery disease (no angina or recent myocardial infarction) and valvular heart disease who underwent F-GP1 cardiac PET-CT as part of a concurrent study (NCT04073875) (34).

#### **4.1.1 Cohort 1: Patients with myocardial infarction with non-obstructive coronary arteries**

We will recruit 50 patients with myocardial infarction and non-obstructive coronary arteries on coronary angiography

#### **4.1.2 Cohort 2: Patients with coronary causes of type 2 myocardial infarction**

We will recruit 10 patients with coronary artery thromboembolism and 10 patients with spontaneous coronary artery dissection. Finally, we will include 10 subjects who have had iatrogenic coronary artery dissection or intramural haematoma as a complication of their percutaneous coronary intervention.

### **4.2 INCLUSION CRITERIA**

- Males and females ≥ 18 years of age

- Clinical presentation of chest pain, ST-segment deviation within a coronary artery territory on the electrocardiogram, raised cardiac troponin and non-obstructive coronary arteries on invasive coronary angiography as per international societal diagnostic criteria (19, 26).

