### **13.2 MANAGEMENT OF PROTOCOL NON COMPLIANCE**

#### **13.2.1 Protocol Waivers**

Prospective protocol deviations, i.e. protocol waivers, will not be approved by the Sponsors and therefore will not be implemented, except where necessary to eliminate an immediate hazard to study participants. If this necessitates a subsequent protocol amendment, this should be submitted to the REC and local R&D for review and approval if appropriate.

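### The single, unlabelled inclusion list in section 4.2 requires non-obstructive arteries, but section 4.1.2 recruits 30 cohort 2 patients with no such condition, so 4.2 can exclude patients the protocol plans to enrol

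*Protocol*

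**What the plan says.** Section 4.1 announces that "We will recruit two patient populations after invasive coronary angiography has been completed", and its subsections describe them differently.

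- **Cohort 1 (4.1.1):** "We will recruit 50 patients with myocardial infarction and non-obstructive coronary arteries on coronary angiography".
- **Cohort 2 (4.1.2):** 10 patients with coronary thromboembolism, 10 with spontaneous coronary artery dissection, and "10 subjects who have had iatrogenic coronary artery dissection or intramural haematoma as a complication of their percutaneous coronary intervention". Nothing is said about the degree of stenosis in any of the three groups.

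Section 4.2 is the only inclusion list and has no cohort label. It has two items. One is adult age. The other is a clinical presentation with chest pain, ST-segment deviation in a coronary territory, "raised cardiac troponin and non-obstructive coronary arteries on invasive coronary angiography as per international societal diagnostic criteria". The elements of the second item are joined by a single conjunction, so all must be present. Section 1.1.4.1 gives the meaning of non-obstructive: no stenosis of 50% or more.

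Section 13.2.1 says that "protocol waivers, will not be approved by the Sponsors and therefore will not be implemented", with an exception only for an immediate hazard to participants.

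**The concern.** Eligibility lists are applied literally at screening, and the schedule in section 6.9 has one eligibility check for everyone. A cohort 2 patient whose angiogram shows a stenosis of 50% or more fits the recruitment plan in 4.1.2 and fails 4.2. Enrolling that patient departs from 4.2; refusing the patient departs from the intent of 4.1.2. Because waivers are barred, screening staff cannot settle the matter by judgement. At stake is whether the trial can enrol the groups it names without protocol deviations, and whether each cohort 2 group is recruited on its intended definition or on a narrower one.

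A lesser question arises at the boundary between the cohorts. A recognised embolism or dissection with non-obstructive arteries can fit both descriptions, and no sentence states which cohort takes the patient. The primary objective (2.1.1) asks for the frequency of thrombotic causes in infarction with non-obstructive arteries, so readers need to know whether such patients belong to the population described.

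**Working it through.** **Planned numbers.** From 4.1.1 and 4.1.2: 50 + 10 + 10 + 10 = 80 patients, of whom 10 + 10 + 10 = 30 are in cohort 2. The share whose description in 4.1.2 carries no stenosis condition is 30/80 = 37.5%; the iatrogenic group alone is 10/80 = 12.5%. These are sizes of groups, not counts of patients excluded.

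**Testing both readings of 4.2.**

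1. *4.2 covers everyone.* The list is unlabelled, follows directly on the description of both cohorts, and section 5.1 treats identification for all cohorts together. On this reading, any cohort 2 patient with a stenosis of 50% or more is ineligible, although 4.1.2 would admit that patient.
2. *4.2 covers cohort 1 only.* The conflict then disappears, but the protocol does not say this, and cohort 2 has no inclusion criteria beyond the diagnoses named in 4.1.2.

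Either way the text needs correcting: under the first reading the sections conflict, and under the second a label is missing and cohort 2 has no list of its own.

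**How many patients could be barred under reading 1.**

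- *Iatrogenic group (10).* These patients are defined by a complication of a percutaneous coronary intervention. This is the clearest mismatch, although 4.1.2 does not state lesion severity here either.
- *Embolism and spontaneous dissection (20).* Section 1.1.4.2 says embolism produces infarction with non-obstructive arteries "if it involves the microcirculation or if the epicardial coronary thrombus is not associated with atherosclerotic coronary artery disease". Section 1.1.4.3 says the arteries in spontaneous dissection may look normal or nearly so. Some or all of these 20 may therefore satisfy 4.2.
- *Bounds.* The protocol gives no distribution of stenosis in any of the three groups. The number barred is therefore between 0 and 30, and the documents do not narrow it.

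**The boundary between cohorts.** The text points two ways.

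- *Towards cohort 2.* Section 4.2 invokes the criteria in references 19 and 26. Section 1.1.4.1 attributes to those same two references the condition of "no specific alternative diagnosis for the clinical presentation". Cohort 2 is also named by diagnosis, and section 2.2.2 lists thrombosis-related type 2 causes separately.
- *Towards cohort 1.* Section 1.1.4.1 says of infarction with non-obstructive arteries: "This includes patients presenting with either type 1 or type 2 myocardial infarction". Section 1.1.4.2 counts embolism within it in the circumstances quoted above.

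The expert panel in 6.8 classifies infarction subtype and does not assign a cohort.

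**The case against.** The strongest reply is that an informed reader knows what is meant: the non-obstructive requirement appears in the description of cohort 1, so 4.2 was written with cohort 1 in mind. That may well be the intention. But 4.1.1 states the requirement for cohort 1 without saying that it applies to no one else, and nothing in 4.2 limits its reach. An intention that has to be inferred does not settle a screening check when waivers are barred. Nor would a statistical analysis plan cure this, because who may be enrolled is fixed in the protocol.

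The reply on allocation is better and largely stands. Through the criteria it cites, 4.2 carries the condition that no other diagnosis explains the presentation, and this points recognised embolism or dissection to cohort 2. The statements pointing the other way are background on aetiology, not enrolment rules. Allocation is therefore a matter for clarification, not a second contradiction.

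Three stronger readings might be inferred, and the documents support none of them.

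- *That all 30 cohort 2 patients (37.5%) are ineligible.* Those with non-obstructive arteries and the other listed features would pass, and their number is not stated.
- *That the cohort 1 frequency could have a denominator anywhere from 50 to 70.* Section 4.1.1 fixes cohort 1 at 50. Admitting recognised cases would change who makes up the 50, not enlarge it.
- *That the thrombosis frequency shifts or power is lost.* Any such figure needs an assumed number of recognised cases and an assumed tracer-positive rate among them, and the protocol gives neither.

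**Conclusion.** The mismatch between 4.2 and 4.1.2 is real and should be corrected. Followed as written, the only inclusion list can exclude patients whom the recruitment plan names, and the waiver rule closes the informal way out. It potentially touches the 30 cohort 2 places out of 80, most clearly the 10 iatrogenic ones; the number actually barred is unknown, from 0 to 30. This rests on reading 4.2 as covering all participants, which is what an unlabelled list says, and on the 50% definition in 1.1.4.1. Confidence is high.

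The missing allocation sentence is a clarification only, held with moderate confidence because the cited criteria already lean towards cohort 2. The formal primary endpoint (2.2.1) remains the target to background ratio, and the planned numbers are unaffected.

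**What to change.** Amend sections 4.1 and 4.2 as follows.

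- State the inclusion criteria separately for each cohort, and within cohort 2 for each of its three groups where they differ. Tie the non-obstructive requirement explicitly to the cohort or cohorts it is meant for, and do the same for chest pain, ST-segment deviation and raised troponin. Which way the sections are reconciled is for the investigators; 4.2 and 4.1.2 must then agree.
- Add one sentence saying which cohort takes a recognised embolism or dissection with non-obstructive arteries, so that the population behind the frequency in the primary objective is clear.

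The cost is a short amendment through the route in section 13.1. The 50 and three times 10 places stay as they are, and no study procedure changes.
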